3 STUDY OBJECTIVES AND ENDPOINTS

Primary Objective	Primary Endpoints

 To evaluate the safety and tolerability of viltolarsen administered IV at weekly doses of 80 mg/kg in ambulant and non-ambulant boys ≥ 8 years of age with DMD 	
 Vital signs Physical examination Renal ultrasound Echocardiogram Clinical laboratory tests 
 Hematology and clinical chemistry Urinalysis Urine cytology 12-lead electrocardiogram (ECG) Anti-viltolarsen antibodies Anti-dystrophin antibodies TEAEs and SAEs
Secondary Objective	Secondary Endpoints

 To compare the efficacy of viltolarsen administered IV at weekly doses of 80 mg/kg over a 48-week Treatment Period versus natural history controls in ambulant and non-ambulant boys ≥ 8 years of age with DMD 	
 Peak Expiratory Flow (PEF) Forced Vital Capacity (FVC) Forced expiratory volume in 1 second (FEV1) PUL Brooke scale Vignos scale Hand-held dynamometer NSAA
Exploratory Objectives	Exploratory Endpoints

 To evaluate health-related quality of life impact of viltolarsen treatment on patient's DMD 	
 Treatment Satisfaction Questionnaire (TSQM) Pediatric Outcome Data Collection Instrument (PODCI) Personal Adjustment and Role Skills Scale, 3rd edition (PARS III) Questionnaire

 To evaluate strength of cough in patients with DMD 	
 Peak Cough Flow (PCF)

 To evaluate preservation of ambulation of patients with DMD 	
 Loss of ambulation

 To evaluate daily activity and sleep-wake patterns to explore impact of viltolarsen treatment on patient's DMD 	
 Accelerometry measures of activity and sleep-wake patterns

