9.18.4 Other Assessments

9.18.4.1 Actigraphy (ActiGraph GT9x)

During the Screening process and prior to baseline assessments, patients will be provided with an ActiGraph GT9x, specific information regarding the device, and the wear protocol. Patients will wear the ActiGraph on their non-dominant wrist throughout the study period (10 hour daytime + full nighttime wear). Daily bouts of activity (energy expenditure) and percent sleep efficiency, nighttime awakenings, and duration of nighttime awakenings will be explored through the ActiLife data analyses software platform. Sleep-wake activity analyses will be performed using R*Studio and nparACT software to compute several non-parametric measures from raw actigraphy data. Specifically, the interdaily stability, intradaily variability, and relative amplitude of activity will be computed to explore sleep-wake activity rhythms (circadian rhythmicity) in study patients.

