12.2 Determination of Sample Size

Assuming a sample size of 20, at least 1 adverse drug reaction with an incidence of 15% may be detected at a probability of $\geq 95\%$ for the safety profile, which is the primary outcome. Based on this, it was decided that 20 patients should be enrolled to confirm safety. A minimum of 8 ambulant patients will be enrolled.

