12.6.2.5 ActiGraph GT9x

Validity will be explored through correlation of all clinical strength and function tests and patient reported outcomes with raw data obtained from the AGT9x during clinical testing. Information such as steps, speed, body position/location (using vector magnitude per minute data) will be derived from the raw data; relationships with clinical tests will result from data conversions, descriptive analysis, and correlations with the raw data. Additionally, raw data will be analyzed throughout the study to explore changes in activity and sleep-wake patterns. Throughout the full study, 2-week bouts of continuous data will be analyzed through R*Studio (version 3.5.1, Vienna, Austria) and the nparACT package (version 0.8) to determine sleep-wake rhythms. Sleep-wake rhythms are measured as intradaily variability (quantifies the frequency and extent of transitions between periods of rest and activity on an hourly basis) and relative amplitude (derived from the normalized difference between the most active 10-hour period and least active 5-hour period in an average 24-hour pattern). Raw data will also be analyzed with ActiLife software to identify and score sleep periods defined as nightly percent sleep efficiency (total time in bed/total time asleep), average number of nightly awakenings (mean number of nightly awakenings longer than 3-minute durations), and average duration of nightly awakenings (mean duration of nightly awakenings that are longer than 3 minutes). Effect sizes to determine the magnitude of differences in change over time will be computed.

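### Section 12.6.2.5 defines percent sleep efficiency as the inverse ratio; if that formula is used, its change over time would almost always have the wrong sign

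*Combined protocol and SAP*

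**What the plan says.** The protocol lists "Accelerometry measures of activity and sleep-wake patterns" as an exploratory endpoint (Section 3). The procedures text, Section 9.18.4.1, says that "percent sleep efficiency, nighttime awakenings, and duration of nighttime awakenings will be explored through the ActiLife data analyses software platform", and gives no formula.

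The analysis text, Section 12.6.2.5, says "Raw data will also be analyzed with ActiLife software to identify and score sleep periods" and then lists the measures, the first being "nightly percent sleep efficiency (total time in bed/total time asleep"). This is the only place where a numerator and denominator are given. The same section ends its plan for these data with "Effect sizes to determine the magnitude of differences in change over time will be computed". No direction of benefit is stated for sleep efficiency.

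**The concern.** An efficiency expressed as a percent should lie between 0 and 100 and rise as sleep improves. The printed ratio does neither. Because it is the only formula in the documents, a programmer or report writer looking for the definition would find the inverse.

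The planned output is an effect size for change over time, so the sign matters. If the printed ratio is applied, worsening sleep would normally be reported as a gain in efficiency, and improvement as a loss. The documents do not say whether the ActiLife output or the written definition governs.

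Nothing else is affected: the number and duration of awakenings, the rhythm measures, the primary safety analysis and the secondary efficacy analyses do not use this ratio.

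**Working it through.** The plan states no figure for sleep efficiency, so there is none to reproduce. The check compares the printed ratio with its inverse.

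**Inputs.** From the documents: the printed ratio (Section 12.6.2.5) and n = 20 (Section 12.2). Assumed, because the documents give no values: time in bed, time asleep, baseline level, SDs and size of change.

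**Range.** Let B be time in bed, A time asleep, and E = A/B. Since A ≤ B, E ≤ 100%. The printed measure is B/A = 1/E, which is therefore at least 100% and unbounded above.

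**One patient.** 1/E falls whenever E rises, so any non-zero change reverses sign. Going from 1 h to 3 h awake:

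| Time in bed (assumed) | Printed, B/A | Change | Correct, A/B | Change |
|---|---|---|---|---|
| 8.5 h | 113.3% to 154.5% | +41.2 | 88.2% to 64.7% | -23.5 |
| 9.5 h | 111.8% to 146.2% | +34.4 | 89.5% to 68.4% | -21.1 |
| 10.5 h | 110.5% to 140.0% | +29.5 | 90.5% to 71.4% | -19.0 |

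For example, 9.5/8.5 = 1.118 and 9.5/6.5 = 1.462, against 8.5/9.5 = 0.895 and 6.5/9.5 = 0.684.

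**Group mean.** The mean of reciprocals is not the reciprocal of the mean, so reversal is not guaranteed for a group. Two patients moving from 0.60 to 0.66 and from 0.90 to 0.83 show this:

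- Mean change in E: (0.06 - 0.07)/2 = -0.005.
- Mean change in 1/E: [(1.515 - 1.667) + (1.205 - 1.111)]/2 = -0.029, the same sign.

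To see how often this happens, 40,000 groups of 20 were simulated per setting. Baseline was normal with mean 88% and the stated SD. Follow-up was baseline plus a normal change with the stated mean and the same SD. Values were bounded at 40% and 100%, and the printed value is 10,000 divided by the correct percent.

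- With SD 5, a true mean change of -5 points becomes about +7.4 points as printed. The standardised change (mean change divided by SD of change) is -1.05 correct and about +1.02 as printed: similar size, opposite sign.
- Share of groups in which the two definitions agree in sign, that is, no reversal:

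| True mean change | SD 3 | SD 5 | SD 8 |
|---|---|---|---|
| 0 | 6% | 9% | 9% to 10% |
| -1 | 2% | 4% to 5% | 6% |
| -3 | under 0.1% | 0.1% | 1% |
| +1 | 2% | 7% | 11% to 12% |
| +2 | 0.1% | 3% | 10% to 11% |
| +3 | under 0.1% | 0.5% to 0.7% | 7% |

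Ranges reflect repeated runs. The higher shares for improvement at SD 8 arise partly because values are capped at 100%, which pulls the realised mean change towards zero.

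A second simulation with other assumptions (mean efficiency 0.75 to 0.85, between-patient SD 0.05 to 0.10, within-patient SD 0.03 to 0.06) gave reversal in 96.9% to 100% of groups for true changes of 0.02 to 0.05 in size, and in 93.3% with no true change.

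**The case against.** The strongest reply is that the printed ratio may never be computed. Sections 9.18.4.1 and 12.6.2.5 both give the scoring to ActiLife, so the parenthesis may only describe a software output. If that output is time asleep over time in bed and is used unchanged, no number changes. This stands, and the concern is conditional for that reason. But the documents do not give ActiLife's formula, so they do not settle the matter either way, and the printed definition would still mislabel the result in a table or report.

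Two further points lower the risk. Values at or above 100% for every patient would probably be noticed. And Section 12.1 provides for an SAP, to be finalized before database lock, that supersedes the protocol where they differ. Both are chances to catch the error. Neither corrects the definition, and a reversal of direction agreed after the data have been seen is harder to defend than one made beforehand.

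It is also fair to say that the simulated sizes rest wholly on assumed values, and that reversal is less frequent for small improvements with a wide spread. The inversion itself depends on none of these assumptions.

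**Conclusion.** The definition is wrong as written; the severity is minor. That the ratio is inverted follows from the text alone. If it is applied, the sign reversal is certain for a single patient. For the mean of 20 it is very likely: about 88% or more of simulated groups in every setting tried, and at least 99% when sleep worsens by 3 points or more under the first model's assumptions. The raw size of the change is also altered, while the standardised size is nearly unchanged in the -5 point example. Whether any reported result would be wrong depends on how the ActiLife output is computed and used, which the documents leave open. The damage is confined to one exploratory measure with no test or threshold attached.

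**What to change.** In Section 12.6.2.5, and in the SAP, define percent sleep efficiency as 100 x total time asleep / total time in bed. State that higher values mean better sleep. Confirm before database lock that this matches the variable exported from ActiLife. The cost is two terms swapped and one clause added; no data collection and no other analysis changes.

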12.7 Pharmacokinetic Endpoints and Analysis

Population PK analyses will be presented in a separate report.

12.7.1.1 Antibodies and Pharmacokinetics

Antibodies and PK concentrations will be summarized by treatment group over time. PK concentrations may be summarized at a later date.

12.8 Interim Analyses

No interim analyses are planned.

12.9 Handling of Missing Data

Every effort will be made to collect all data. However, despite best efforts, missing or incomplete data may be reported. All missing or partial data will be presented in the patient data listing, as they are recorded on the eCRF.

Patients lost to follow-up or withdrawn will be included in statistical analyses up to the point of their last evaluation. Unless otherwise specified, no imputation of values for missing data will be performed. Of note, since patients with DMD are expected to decline over time, imputing efficacy parameters by last value carried forward mostly biases towards patients appearing stronger or faster than they are, since it carries forward potentially a better value than the value at the time of the missed observation. Therefore, for this study, we will summarize how much data are missing, but do not expect to need to impute any data to accomplish the analyses as described. Details of handling missing data will be described in the SAP.

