9.16.1.5 North Star Ambulatory Assessment

NSAA will be performed by a CE at visits specified in the Schedules of Study Assessments ([Table 1](#) and [Table 2](#)). The NSAA is a clinician-rated, 17-item, functional scale originally designed for ambulant boys with DMD who are able to ambulate at least 10 meters ([Mazzone et al, 2009](#)). This evaluation tool assesses functional activities including standing,

getting up from the floor, negotiating steps, hopping, and running. The assessment is based on a 3-point rating scale of 2 = ability to perform the test normally, 1 = modified method or assistance to perform test, and 0 = unable to perform the test. Thus, total score can range from 0 (completely non-ambulant) to 34 (no impairment) on these assessments. The NSAA will include an assessment of both grade and time for the Time to Run/Walk 10 Meters Test and the Time to Stand Test. Individual test item scores and total score will be recorded in source documents and in the relevant eCRF. This test should take approximately 20 minutes.

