9.16.1.6 Loss of Ambulation

Time to run/walk 10 meters will be assessed as part of the NSAA for patients performing the NSAA. Loss of ambulation will be defined as the inability to perform the Time to Run/Walk 10 Meters Test in ≤ 30 seconds at any post-baseline visit and for all remaining assessments.

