12.6.1.7 North Star Ambulatory Assessment

NSAA will be compared between patients receiving viltolarsen and the historical control group using mixed models with repeated measures. Covariates of age and baseline value will be included. Steroid exposure will be evaluated and included as an additional covariate if necessary.

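### The plan does not say how the NSAA is scored once a boy loses ambulation; if it is left missing in either group, the comparison with historical controls is biased

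*Combined protocol and SAP*

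**What the plan says.** **The scale.** Section 9.16.1.5 describes the NSAA as a "functional scale originally designed for ambulant boys with DMD who are able to ambulate at least 10 meters". An item that a boy cannot do scores 0, and the "total score can range from 0 (completely non-ambulant) to 34 (no impairment").

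**Who is tested.** Table 1 (footnote x) and Table 2 (footnote s) place the NSAA in the function and strength battery. The visit lists in Section 10 name it at Screening, Pre-Infusion, Weeks 13, 25, 37 and 49, and early termination. None of these limits it to ambulant boys or stops it at loss of ambulation. Section 9.16.1.6, however, says that the timed 10 m test "will be assessed as part of the NSAA for patients performing the NSAA", which implies that some patients do not perform it. That section defines loss of ambulation as failing to complete 10 m within 30 seconds at a post-baseline visit and at every later one.

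**The analysis.** Under Section 12.6.1.7, "NSAA will be compared between patients receiving viltolarsen and the historical control group" by mixed models with repeated measures, adjusted for age and baseline.

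**Missing data.** Section 12.9 leaves room for exceptions but otherwise says that "no imputation of values for missing data will be performed", adds that the authors "do not expect to need to impute any data to accomplish the analyses as described", and closes with "Details of handling missing data will be described in the SAP". The supplied document holds no statistical plan beyond Section 12, and nothing in it specifies otherwise for the NSAA.

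**The controls.** Section 2.2.2 says that the natural history study ran from 2006 to 2016 with annual visits. Section 12.6.1.8 expects 16 to 32 controls with evaluations 6 to 15 months apart.

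**The concern.** Loss of walking is the largest decline that the NSAA can record. If the test is skipped once a boy can no longer walk, his later scores are missing because of the outcome itself. A mixed model treats missing values as predictable from what was observed, so it continues his milder earlier course. Section 12.9 rejects last value carried forward because it makes declining boys look better than they are; leaving these values missing errs the same way.

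The two groups are exposed differently. A treated boy who loses ambulation late may keep his Week 13, 25 and 37 scores. A control seen once a year may contribute no follow-up score at all. The trial schedule cannot govern how controls were tested, since their data already exist.

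At stake is the NSAA comparison, where as few as 8 trial boys may be ambulant (Section 12.2), so one or two cases matter.

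**Working it through.** **1. The plan's own figures.** The plan states no NSAA mean, SD, decline, effect size, power or rate of loss. Its one numerical design figure concerns safety and reproduces: 1 − 0.85^20 = 0.961, against the stated 95% or more. It does not bear on the NSAA. Every NSAA input below is therefore assumed, and the results illustrate a mechanism.

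**2. The text, group by group.**
- *Trial boys.* If Tables 1 and 2 are followed and items that cannot be done score 0, nothing is missing. If Section 9.16.1.6 is read as letting non-walkers skip the test, the score is missing and stays so by default. The two readings are not reconciled.
- *Controls.* No section says whether a control who had stopped walking was tested, scored 0 or left blank, or how a blank is handled.

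**3. Effect on a group mean.** Assume n ambulant boys, of whom k lose ambulation. The rest lose 3 points, and the k boys fall from a baseline b of 6 to 10 down to 0. Scored 0, the mean change is −[(n − k) × 3 + k × b] / n. Left missing, it is −3.0.

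| n | k = 1 | k = 2 | k = 3 |
|---|---|---|---|
| 8 | −3.4 to −3.9 | −3.8 to −4.8 | −4.1 to −5.6 |
| 12 | −3.3 to −3.6 | −3.5 to −4.2 | −3.8 to −4.8 |

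Example: n = 8, k = 1, b = 6 gives −(7 × 3 + 6)/8 = −3.4. Decline is understated by about 0.3 to 2.6 points.

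**4. Does a mixed model repair it?** Simulation, 150 runs per setting: 10 treated boys and 24 controls, four visits over a year in both groups, baseline mean 18 (SD 5), slope −3 a year (SD 1.5), loss only in boys with baseline below 18, and a score of 0 after loss. The drug has no effect on boys who keep walking. The model has a random intercept and adjusts for baseline and age.

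| Loss, treated vs control | 1-year difference, left missing | Scored 0 |
|---|---|---|
| 10% vs 10% | −0.1 | 0.1 |
| 20% vs 20% | 0.1 | −0.1 |
| 10% vs 25% | −0.1 | 1.7 |
| 25% vs 10% | 0.0 | −1.9 |

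Simulation standard errors are about 0.07 (missing) and 0.12 to 0.15 (scored 0). Rough check: boys with baseline below 18 average about 18 − 0.8 × 5 = 14, so loss costs about 14 − 3 = 11 points more than continued walking, and (0.25 − 0.10) × 11 = 1.65. The model removes this difference in whichever direction it lies.

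**5. Unequal visit schedules.** A second mixed-model check used four treated visits, one control visit and a random slope (100 runs per setting). It assumed baseline 16 (SD 6), decline 4 a year (SD 3), a true effect of 2 points a year, and loss when the underlying score reaches a threshold. From scored 0 to left missing, the 48-week difference moved as follows:
- threshold 6, 8 vs 12 boys: 1.97 to 1.52 (0.45/1.97 = 23%);
- threshold 6, 12 vs 20 boys: 2.04 to 1.50 (0.54/2.04 = 26%);
- threshold 4, 12 vs 20 boys: 1.71 to 1.47 (0.24/1.71 = 14%).

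With no drug effect the estimate moved from −0.15 to −0.43.

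**6. Is 0 the right benchmark?** A boy who fails the 30-second test can still earn points on other items. With the same assumed inputs, differences in mean 48-week change (one million draws per setting; a plain comparison of means, not the mixed model) are:

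| Threshold | Residual scores kept | Scored 0 | Dropped |
|---|---|---|---|
| 4 | 1.83 | 1.89 | 1.75 |
| 6 | 1.84 | 2.04 | 1.72 |

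Dropping loses 0.08/1.83 = 4% to 0.12/1.84 = 7%. Forcing 0 adds 0.06/1.83 = 3% to 0.20/1.84 = 11%. Part of the gap between scoring 0 and leaving missing therefore comes from the severity of the 0, and observed totals should never be overwritten.

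**The case against.** The strongest reply is that nothing need be missing. The schedule asks for the NSAA in every patient at every function visit, and Section 9.16.1.5 gives 0 to an item that cannot be done. A boy who has stopped walking is then assessed and scored low. The phrase in Section 9.16.1.6 may refer only to boys non-ambulant at entry. This stands for trial boys if sites read it so, but the protocol does not say so, and it cannot settle how controls were assessed.

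Section 12.9 also allows exceptions and defers details to the SAP, which Section 12.1 says will be finalised before database lock and will supersede the protocol. That stands too: a rule may come there. It makes this a request for text in that place, not proof that none will be written.

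Finally, the Vignos scale separates ambulant from non-ambulant boys (Section 9.16.1.3) and is compared with controls, and loss of ambulation is an exploratory endpoint. This limits the importance of the gap. However, Section 12 gives no analysis of loss of ambulation and does not link it to the NSAA.

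**Conclusion.** The point holds in conditional form. The plan does not state whether the NSAA is performed and scored after a boy ambulant at baseline loses ambulation, in the trial or among the controls. If it is not done, the default leaves a gap caused by the outcome, and the planned mixed model does not correct it. The risk is greater for the controls, whose data already exist and who were seen about once a year.

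A reader might infer that the largest declines do drop out of the comparison. The documents do not support that: the schedule and item scoring may capture them in trial boys, and how controls were tested is not described. A reader might also infer that a real drug effect would be shrunk by a known percentage. That is not supported either. The direction depends on which group loses ambulation more often, and the percentages in steps 5 and 6 rest on assumed inputs and partly on the severity of a 0. The size cannot be derived from the documents.

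The NSAA is one of eight secondary endpoints in a study whose primary outcome is safety; the primary result is unaffected.

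**What to change.** Add to Sections 12.6.1.7 and 12.9, and carry into the SAP before database lock:

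> For patients ambulant at baseline, trial or control, NSAA is attempted and scored at every function visit, with items the patient cannot perform scored 0; any observed total is used as recorded. Where NSAA was not done because ambulation had been lost, the total is set to 0 at that visit, in both groups. NSAA missing for other reasons is not imputed. A sensitivity analysis leaves these values missing.

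For the controls, attempting the test cannot be required after the fact, so there only the scoring and missing-value parts apply. The SAP should also say how loss is recognised in them; a Vignos grade of 7 or more at the same visit is one marker that the protocol already defines as non-ambulant. Section 9.16.1.6 should say which patients perform the NSAA.

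The cost is one rule and one extra analysis, with no new data. The downside is that 0 may be slightly severe for a boy who could still earn points on standing items; limiting it to visits without an observed score contains this, and the sensitivity analysis shows its influence. Fixing the rule before results are seen matters here, because in an open-label, externally controlled study a later choice could look like picking the favourable one.
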